8. STUDY PROCEDURES AND DATA COLLECTION

2-DIMENSIONAL DOPPLER ECHOCARDIOGRAPHY. **Procedure:** Participants will be studied by one of two senior sonographers during quiet respiration in the left lateral decubitus position with administration of intravenous agitated saline to enhance imaging. Parasternal, apical and subcostal 2-D views and apical 3D views will be obtained with transducer orientation and gain settings adjusted to optimally define endocardial surface of each cardiac chamber. Measurements will be performed by the Director of the ECHO Lab (accredited by the Intersocietal Commission for the Accreditation of Echocardiography Laboratories), [name] (Co-I) and designate off-line (HeartLabs Inc, Q Labs, Phillips Medical) in a blinded fashion on 3 representative beats and the results averaged. Measurements will be performed according to the American Society of Echocardiography recommendations ^{79,80}. Studies will be archived on CD. Rigorous quality control measures will be used including random repeat measurements to calculate inter- and intra-observer reliability.

Approximately 20% of echocardiograms result in suboptimal views in at least 2 of 6 myocardial segments of the left ventricle in apical views. The use of a contrast agent can opacify the sub optimally viewed areas allowing for better analysis. Individuals with obesity, lung disease, or other critical care areas usually require the use of a contrast agent for optimal echocardiogram views. Subjects requiring a contrast dye will be administered an IV dose of Definity ® (perflutren lipid microsphere injectable suspension), a US Food and Drug Administration (FDA) approved contrast dye. Subjects will be screened for known contraindications: known or suspected cardiac shunts or patent foramen ovale, or known hypersensitivity to perflutren. Subjects will also be informed of the potential risks

associated with Definity ® as described in the informed consent document.

Relevant ECHO Variables:

- 1) Left and Right Atrial Parameters: Left atrial volume by using the biplane area-length method ⁷⁹, right atrial area (from the 4-chamber view), left atrial pressure estimated from the ratio of early diastolic transmural flow velocity to early annular tissue velocity ⁸¹ and right atrial pressure based on the diameter of the inferior vena cava and its response to a "sniff" will be assessed ⁸². Peak left atrial systolic strain, a measure of LA remodeling which is inversely related to fibrosis in PAF ⁸³, will also be measured.
- 2) Left Atrial Appendage (LAA) Parameters: LAA wall motion velocity, a measure associated with AF will be assessed ⁸⁴. A value of >40 cm/s, has been noted to be an independent predictor of NSR maintenance in AF⁴⁴. LAA tissue velocity, a more readily obtained and sensitive LAA dysfunction measure will also be measured ⁸⁴.
- 3) Left ventricular ejection fraction (LVEF, %): This will be derived from left ventricular end-diastolic volume (LVEDV) and end-systolic volume (LVESV): $[(\text{LVEDV} - \text{LVESV}) / \text{LVEDV} \times 100]$ ⁸⁵.
- 4) Left ventricular mass index (LVMI): This will be calculated by a validated formula ⁸⁶ : $\text{LVMI} = \{0.8 \times [1.04 \times (\text{LVIDd} + \text{IVST} \times \text{LVPWT})^3 - (\text{LVIDd})^3] + 0.6\} / \text{height}^{2.7}$, where LVIDd is LV internal diastolic diameter, IVST is interventricular septal thickness and LVPWT is LV posterior wall thickness, measured in centimeters.
- 5) Left ventricular hypertrophy (LVH): Using previously published thresholds, we will define LVH as an LVMI of 49.2 g/m^{2.7} for men and 46.7 g/m^{2.7} for women ⁸⁷. Subjects with LVH will be classified as having concentric hypertrophy if relative wall thickness $[(\text{LVPWT} \times \text{IVST}) / \text{LVIDd}]$ is >0.41 or eccentric hypertrophy if ≤ 0.41 ⁸⁸.

2) POLYSOMNOGRAPHY (PSG). *Procedure for PSG*: Research PSG will be performed using the Compumedics E-series system (Abbott'sford, AU) which will include 3 cortical encephalograms, bilateral electro-oculograms, a bipolar submental electromyogram, thoracic and abdominal respiratory inductance plethysmography, airflow (by nasal-oral thermocouple and nasal cannula pressure recording), oximetry (using highly sensitive finger pulse oximeter, sampling frequency 25Hz), electrocardiogram (ECG) at 250Hz (used to derive HRV measures of autonomic function); body position (mercury switch sensor), bilateral leg movements. EEGs are recorded at 125Hz. Sensors will be calibrated, and signal quality/impedance checked by a certified technician, using standardized techniques. PSG scoring criteria are documented in the Case Sleep Research Manual of Procedures (**Appendix B**). ***Relevant PSG Variables***: Apneas will be classified as "central" or "obstructive" according to the absence or presence of respiratory effort respectively. Hypopneas will be scored as a 50% amplitude reduction in inductance or flow and associated 3% oxygen desaturation or arousal. Periodic breathing will be defined as airflow or inductance channels increasing and decreasing at least 50% from the maximum, in a cyclic waxing and waning or "sinusoidal" manner for a consecutive period of ≥ 10 min.

Procedure for PSG ECG Signal Extraction: ECG monitoring data from the PSG Baseline and Follow Up Exams will be processed and analyzed by the Case Electrophysiology Core (Director: [name], Nord Professor of Engineering). Data will be exported as European Data Format (EDF) ECG files into customized Matlab programs that

will allow application of time and spectral-based algorithms for extracting quantitative ECG measures. Data will be closely inspected and edited using graphical tools. Artifact cleaning will be performed and those periods of NSR in the ECG recording will be identified and scored to perform HRV analyses based upon automated algorithms developed by the Case Engineering group. Random sampling for manual scoring will be performed to confirm agreement and accuracy of artifact scoring and identification of NSR periods performed by automated tools. A dataset of ECG marker output will be generated and merged with the rest of the study data for statistical analyses. HRV analyses (time and frequency domain) will be performed with ECG signal processing tools developed by [name], which are efficient, robust and account for artifact. We will use algorithms and automated methods of feature extraction that have been validated in both synthetic and published data^{89, 90}, account for varying signal to noise ratio and non-stationary data and have artifact rejection capability. We selected ECG measures as informed by existing literature, AF pathophysiology and reliable extraction; however, other markers will be analyzed for which we have developed algorithms (i.e. non-linear indices such as conditional entropy). **Relevant PSG ECG Variables:** **ECG measures will be based upon NSR periods identified by automated analyses with manual over-reading of random segments.* HRV, considered to measure sympathovagal modulation of heart rate, will be quantified using standard time domain methods [time intervals between normal beats (SDNN), the root mean square differences between adjacent normal beats (r-MSSD), the % of pairs of adjacent beats differing by >50 ms (pNN50)], and with frequency spectral based measures which mathematically deconstruct heart beat patterns into underlying rhythmic components using Fast Fourier transforms: low (0.04-0.15 Hz) and high (0.15-0.4 Hz) frequency bands ratio (LF/HF). Standardized approaches will be used⁹¹ with close editing for artifact and ectopy. ECG recordings with >20% ventricular ectopic beats will be excluded from analyses⁹². Graphical analysis will include *5-min averaged heart rate (HR) patterns, hourly power spectral analysis, hourly Poincaré plots and beat-by-beat HR tachograms*. As there is no consensus whether respiratory variation reflected in the ECG signal offers useful physiologic information vs. introduction of artifact, we will perform sensitivity analyses with unadjusted and “adjusted” respiration time series analyses⁹³. To assess ECG measures independent of respiratory artifact, a 5 min ECG period will be selected and restricted to normal breathing during wakefulness at the beginning, and also at the end of the PSG. ECG markers will be analyzed as continuous outcomes, averaging information from 5 min intervals of NSR periods deriving an aggregate summary of electrophysiological variability. To take into account sleep state, 5-min ECG windows during sleep vs. wake will be selected for analyses. ECG analyses will be performed on concatenated epochs (30 sec windows): 1) Epochs with apneas/hypopneas vs. those without, 2) REM vs. NREM epochs and 3) Epochs with EEG arousals vs. those without.

3) 7-21 Day CONTINUOUS ECG MONITORING.

Procedure: A 3-lead (2 channel), wireless, lightweight (3.2 ounce) ECG monitoring device (Heartrak External Cardiac Ambulatory Telemetry ®) will be used to collect the ECG data over a 7-21 day period in those with PAF after the baseline and follow-up DCRU/CRU visits. The device is: 3x7", bandwidth: 0.05-30 Hz, sampling rate=205 Hz, stores 30 days of

data, 30 feet transmission mode and memory hold of 10 years with a <1% data transmission failure and data loss in field testing. 7-21 day was chosen given the variability of PAF and because ECG monitoring >48 hours is reasonable to capture AF paroxysms ⁹⁴. **ECG Sensor Application**. This will be performed by a trained technician. Participants will be asked to remove clothing from the waist up to attach the sensors to the chest. Staff will ensure privacy by covering the participant with a sheet or gown. The staff will shave necessary areas on the chest prior to sensor application to ensure that the sensors stick closely to the skin and will provide the participant with the ECG monitor/holster/clip, leads, communicator and charger, electrodes and a handbook with simple pictorial/written educational instructions.

At-home ECG Monitoring Logistics. The ECG monitor box may be clipped to a belt or pocket, and the communicator may be placed in a pocket (much like a cell phone). The participant will be instructed to engage in usual activities and instructed to remove the monitor before bathing and reapply the sensors after bathing. An ECG technician will be available by phone 24-7 to address issues with device malfunction, lead placement and replacement of equipment. Research staff will contact the participants every 3-4 days to assess for symptoms and help troubleshoot any mechanical or logistical issues. ECG quality grade data will be collected: (excellent: >90% of ECG data without artifact, good: 70-90% without artifact, fair: 50-70% without artifact, poor <50% artifact free).

Relevant ECG Variables: AF paroxysm frequency will be scored by a certified ECG technician and categorized by sleep vs. wake states based upon self-report from the ECG log. This will allow for assessment of AF burden temporal patterns via 7-21 day ECG monitoring relative to SDB. These ECG data will also be analyzed by [name] group, including [name] and [name], if there is insufficient NSR data from the PSG ECG to perform HRV analyses.

4) ACTIVITY MONITORING. Procedure: An accelerometer (GT3X+, Actigraph Co., Ft Walton Bch, FL) will be used for 7-21 days, coincident with the time of continuous ECG monitoring, to provide objective measurement of the duration and intensity of physical activity and sleep. Subjects will be instructed to secure the accelerometer on their wrist with an elastic band, wearing it through each day, other than while in the water.

5) FASTING VENIPUNCTURE (52cc). Procedure: Phlebotomy will be performed the morning of the baseline and follow-up visits using standard techniques by trained research staff following written procedures (e.g., pre-labeled bar coded tubes, minimizing trauma, etc.). An intravenous catheter will be placed by the nurse in the morning to perform the blood draw and to facilitate performing the morning ECHO study with agitated saline. The sample will be divided into tubes for the varied analyses (20 mL clot for serum, 20 mL EDTA, 4.5 mL special anticoagulant tube, 5 mL citrate, 2.5 PAXgene). Clots will be centrifuged and the serum removed within 1 hr of venipuncture. Assays will be stored in dedicated, alarmed freezers at -80°C in the DCRU/CRU Core Lab until shipped to the UVM Biochemistry Lab. Extra aliquots designated for future studies will be prepared and stored at -80 °C.

Relevant Biomarker Variables: Assays were selected based upon literature or our own preliminary data. We will investigate the following biological pathways: systemic inflammation [C-reactive protein (hs-CRP), interleukin-6 (IL-6), and soluble IL-6 receptor

(sIL-6R)], oxidative stress (endothelin-1 and oxidized LDL). hs-CRP will be measured using the BNII nephelometry utilizing a particle enhanced immunoassay with intra-assay and inter-assay CVs of 2.1%-5.7%. Circulating IL-6 and sIL-6R will be measured by ultra-sensitive ELISA (R&D Systems with inter-assay CVs 6.3%-15%). Endothelin-1 will be measured by an ELISA test (R&D Systems with inter-assay CV of 6.5% and intra-assay CV of 4.6%). Oxidized LDL will be measured by competitive ELISA (Mercodia Oxidized LDL Competitive ELISA) with intra-assay and inter-assay CV's < 10%. Samples will be run in batch and in duplicate; if they do not agree within pre-specified levels, they are re-run. Because additional aliquots will be saved, other assays will be possible as emerging science identifies their value.

6) DNA collection. Blood will be collected to extract RNA, which will be stored to test future hypotheses regarding genetic determinants of treatment response.

7) OVERNIGHT URINE. Procedure: An overnight urine will be obtained and 3 -1.0 ml, 1 – 9.0 ml plain urine and 1 – 9.0 ml acetic acid aliquots will be stored at -80 °C.

Relevant Biomarker Variable. The proposed measurement for urinary isoprostane 8-epi-prostaglandin F2a, a stable nonenzymatic oxidation product of arachidonic acid ^{95, 96} (expressed as ng/mmol urinary creatinine), is an inexpensive ELISA validated against gas chromatography-mass spectroscopy ⁹⁷ and used in the Framingham Heart Study ⁹⁸, with unpublished data showing its elevation in SDB.

8) ANTHROPOMETRY. *Height (inches, cm)* is measured with the subject in stocking feet, using a wall-mounted stadiometer; *weight (pounds, kg)* with a calibrated digital scale. *Neck circumference (cm)* is determined with a non-stretchable measuring tape (nearest 0.5 cm) while the subject is seated with the head in the Frankfort horizontal plane, measuring below the thyroid prominence, perpendicular to the horizontal axis of the neck. *Waist circumference (cm)* is measured at the smallest area between the lower ribs and iliac crest. *Hip circumference (cm)*

is measured at the widest area around the buttocks. The wrist, abdominal, thigh, calf, and mid upper arm circumferences will also be measured using a non-stretchable measuring tape. *Skinfolds* are measured with calibrated metal calipers from 7 sites (chest, calf, thigh, calf, subscapular, midaxillary, suprailiac, abdominal), using a rotational order, obtaining additional measures if variation >10%.

9) RESTING BLOOD PRESSURE (BP). BP will be measured after the participant has been sitting quietly for at least 5 minutes following standardized guidelines using a calibrated sphygmomanometer. Cuff size will be determined by measuring the circumference of the upper arm, measured at the midpoint and identifying the appropriate bladder size from a standard chart. Measurements will be repeated three times and recorded.

10) QUESTIONNAIRES (Appendix B). The following will be collected: a) The *Berlin Sleep Questionnaire*, a simple 10-item questionnaire that categorizes sleep apnea risk ⁹⁹, b) *Epworth Sleepiness Scale* ¹⁰⁰, a simple 8-item questionnaire to assess sleepiness,

c) The *Sleep Habits and Medical Condition Questionnaire*¹⁰¹, which includes comorbidities, medication use (including anti-arrhythmic medications), caffeine use, smoking, alcohol use, etc., d) The *Medical Outcomes Survey-SF 36 (MOS-SF)*¹⁰², a standardized tool for assessing general health status, physical and social functioning, and fatigue, e) *Patient Health Questionnaire-9 (PHQ-9)*, which assesses depression symptoms. It has ten questions where the answers will be added to indicate severity of depression. The Research Assistant will score depression questionnaires and if the score is indicative of depression (10 or greater) the Research Assistant will then contact a study physician who will determine appropriate referrals and responses and contact the participant to advise him to seek medical/psychiatric consultation. If there was any indication that a participant was in imminent danger to himself or others, the participant would be advised to go to the nearest emergency room for evaluation by a psychiatrist. If signs of depression, anxiety or other psychological disorders were evident without evidence for immediate risk, the participant would be advised to contact a psychologist for further evaluation. f) *Daily ECG/Activity Log*, which will be completed during 7-21 day ECG monitoring including data on sleep/wake times including naps, periods of vigorous activity, caffeine use, alcohol use, smoking, monitor removal time and symptoms (e.g. palpitations, dyspnea, chest pain) g) *Atrial Fibrillation Effect on Quality-of-life*, a 20-item questionnaire that assesses the impact of atrial fibrillation on quality of life.

11) 6 Minute Walk Test. Baseline oxygen saturation and heart rate will be recorded. If oxygen saturation >90%, then proceed with protocol. The patient will walk for 6 minutes down the hall at usual pace. Early termination criteria to stop the test if O2 sat drops to ≤80% for 6 consecutive seconds and/or signs and symptoms of dyspnea, chest discomfort, palpitations or any other concerning symptoms. If the test is terminated before 6 minutes is complete, the distance the patient walked should be documented as the 6-minute walk distance for that test. Heart rate should be recorded concurrently with O2 saturation throughout the entire test. Heart rate and oxygen saturation should be recorded before the start of the study, at the end of the six minute walk and for each minute during the post 3-minute recovery period. Using the BORG Scale record rate the symptoms of breathlessness and leg fatigue. Any medications taken prior to the 6 minute walk will be recorded along with dose and time.

12) Arterial Applanation Tonometry: Arterial Applanation Tonometry is a noninvasive technique that provides the basis for high fidelity analysis of central and peripheral pulse pressures. Waveforms of radial artery recordings will be calibrated with sphygmomanometric brachial artery mean and diastolic pressure measurements. Radial measurements will be performed on the same arm using the SphygmoCor device after sphygmomanometric pressure is obtained with use of an applanation tonometry probe containing a solid state high fidelity Millar transducer over the radial artery with a minimum of two consecutive measurements to obtain pulse wave analysis results. For pulse wave velocity, lead II ECG (LL, LA, RA) will be performed along with carotid and femoral applanation tomometry. Orientation and pressure applied to the transducer will be adjusted to optimize applanation of the artery between the transducer and the

underlying tissue. The pulse wave velocity and pulse wave analysis will be assessed and provide measures of arterial stiffness and indices of subclinical atherosclerosis, and correlated with changes in oxidative stress markers. Waveforms will be processed using the SphygmoCor software (model EM3, version CvMS 9.0, Atcor Medical Pty, West Ryde, Australia.) The applanation tonometry measurements will be obtained the morning of the baseline and 3-month follow-up visits using a standardized protocol.

13) MultiSense™ Monitoring: The MultiSense™ Monitor is a self-contained, reusable, rechargeable, battery-powered, flexible band-aid-like strip, measuring 10.2x3.0 cm (4x1.2 inches), that is capable of detecting and recording a number of correlated physiological parameters. The monitor is taped to the participant's chest using a FDA approved, disposable, double-backed adhesive tape. The device provides a continuous detection and recording, up to 10 days, of high quality ECG signals. The device also provides pulse synchronous measures of blood oxygen saturation and concomitant indices of physical activity and body position (eg. Upright, or lying on back, stomach, right side, or left side). The double-backed adhesive tape insures motionless, waterproof contact between the skin, the electrodes and other sensors of the MultiSense™ Monitor. At the end of the monitoring period, the accompanying software enables a PC to download the recorded data, display, and analyze the data.

The software mentioned above includes an industry-proven arrhythmia-recognition package provided by a 3rd party (Monebo Technologies). It has been thoroughly tested using standard (MIT-BIH/AHA/NST) arrhythmia databases, and has earned FDA 501(k) approval. The software allows automated ECG analysis and interpretation by providing callable functions for ECG signal processing, QRS detection and measurement, QRS feature extraction, classification of normal and ventricular ectopic beats, heart rate measurement, measurement of PR and QT intervals, and rhythm interpretation.

14) Magnetic Resonance Imaging (MRI): An MRI is an electronic picture of your brain created using a strong magnet instead of x-ray energy. The MR scan time will be 60 minutes. The MR scanner makes loud knocking noises. The participant will be provided with earplugs to dull the sounds. A dental impression may be taken of their teeth in order to fashion a bite plate for use during the scan. After the impression is taken, the plate will be fashioned to a device fixed to the table in order to assist in keeping their head from moving during the scan session.

The MRI scan will be performed for research purposes and it is not a complete diagnostic imaging examination. It should not be considered a substitute for a standard clinical MRI evaluation. Because the research MRI cannot exclude abnormalities, no report from the scan will be generated. However, if during the process of reviewing the research MRI an unexpected abnormality is seen, it will be reported to the participant and their physician.

15) Cognitive Battery and Questionnaires (Only for participants with MRI)

A complete comprehensive evaluation of memory and thinking skills will be performed on those that participate in the Magnetic Resonance Imaging sub-study. The cognitive battery includes the Mini Mental State Examination (MMSE), an 11-question measure that tests five areas of cognitive function: orientation, registration, attention and calculation, recall, and language., the Rey Auditory Verbal Learning Test (RAVLT), evaluates verbal learning and memory, the Brief Visuospatial Memory Test (BVMT-R), assesses visual memory, the Symbol Digit Modalities Test (SDMT), evaluates cerebral dysfunction, Trails Making Test A and B, a test of visual attention and task switching, Delis-Kaplan Executive Function System (DKEFS) which measures a variety of verbal and nonverbal executive functions, and the Ruff 2 & 7 Selective Attention Test which measures sustained attention and selective attention.

There will be two questionnaires that the participant will be asked to complete. The Beck Depression Inventory, a 21 question multiple choice questionnaires used for measuring the severity of depression and the Edinburgh Handedness Inventory which is a measurement scale to assess the dominance of a person's right or left handedness in everyday activities.

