10. DATA ANALYSIS

EXPOSURES: *Primary:* 1) SDB defined by AHI, i.e. number of apneas + hypopneas/hour of sleep. *Secondary:* 1) Hypoxia: % sleep time with $\text{SaO}_2 < 90\%$, 2) Obstructive Sleep Apnea [obstructive apneas and hypopneas/hour of sleep, obstructive apnea hypopnea index (OAHI)], 3) Central Sleep Apnea [central apneas/hour of sleep, Central Apnea Index (CAI)], 4) Periodic Breathing and 5) EEG arousals [per hour of sleep, Arousal Index (AI)].

OUTCOME: 1) PAF (SA1) and 2) AF burden defined as frequency of AF paroxysms overall and based on self-reported sleep vs. wake (SA2 and 3)

COVARIATES: Age, race, body mass index (BMI, kg/m^2), waist circumference (cm), anti-arrhythmic/beta blocker/calcium channel blocker/ACE inhibitor/angiotensin receptor blocker medications, pacemaker, defibrillator, heart failure (NYHA class), BP, diabetes mellitus, left atrial volume, LVEF, caffeine use, alcohol use and smoking (current versus never smoker or pack years) and activity level. When assessing hypoxia as the relevant exposure, pulmonary disorders will be included as potential confounders.

Table 2. Mediator (SA1) or Outcome (SA3)

Domain	Primary	Secondary	Rationale
Echocardiographic Measures	Left Atrial Volume (ml/m^2)	LA Pressure, LA Systolic Strain, RA area, RA Pressure, LAA Peak Anterograde Flow Velocity (cm/s), Right Atrial Pressure (mmHg), LVEF, LVMI, LVH (concentric LVMI >0.41 , eccentric ≤ 0.41).	Left Atrial Volume predicts risk of AF and PAF ¹⁰³⁻¹⁰⁶ . Secondary measures also associated with AF.
Autonomic Function (Heart Rate Variability)	SDNN (ms) (Time Domain HRV Measure)	Time Domain (r-MSSD (ms), pNN50), Frequency Domain [LF (Hz), HF (Hz), LF/HF], Graphical Parameters (HR patterns, power spectral analysis, Poincaré plots and beat-by-beat HR tachograms) and Novel non-linear measures (e.g. Conditional Entropy ¹⁰⁷).	Reduced SDNN and LF/HF have been identified as AF triggers ⁴⁰ .
Systemic Inflammation	hs-CRP (mg/L)	IL-6 (pg/ml), sIL-6R (ng/mL)	hs-CRP and IL-6 associated with SDB and AF ⁴⁷⁻⁴⁹ . s-IL6R varies with overnight hypoxia ⁴⁶
Oxidative Stress	Endothelin-1 (pg/ml)	Urinary isoprostane 8-epi-prostaglandin F2a (ng/ mmolCr), Oxidized LDL (U/L)	Endothelin-1 implicated in AF ⁵⁷⁻⁵⁹ . Isoprostane ⁶⁰⁻⁶² and oxidized LDL sensitive to SDB ⁷⁶ .

ANALYTIC METHOD BY AIM.

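### The printed LV mass index and relative wall thickness formulas are dimensionally wrong; coded literally, they would understate LV mass at usual wall thicknesses and miss most LVH.

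*Combined protocol and SAP*

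**What the plan says.** The formulas are in Section 8, under 2-dimensional Doppler echocardiography, Relevant ECHO Variables.

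- **Item 4, LVMI.** The plan introduces the expression with "This will be calculated by a validated formula" and a citation. The cubed term is "LVIDd} + \text{IVST} \times \text{LVPWT})^3", with dimensions "measured in centimeters". In plain notation: LVMI = {0.8 × [1.04 × (LVIDd + IVST × LVPWT)³ − LVIDd³] + 0.6} / height^2.7.
- **Item 5, LVH.** The cuts are: "we will define LVH as an LVMI of 49.2 g/m^{2.7} for men and 46.7 g/m^{2.7} for women". Subjects with LVH are then split by relative wall thickness, printed as "LVPWT} \times \text{IVST}) / \text{LVIDd". Hypertrophy is concentric if the value "is >0.41 or eccentric hypertrophy if ≤ 0.41".
- **Table 2 (Sections 9 and 10).** LVMI and LVH are secondary echocardiographic measures, serving as mediators for SA1 and outcomes for SA3. The table attaches the 0.41 cut to LVMI: "LVH (concentric LVMI >0.41 , eccentric ≤ 0.41".
- **Measurement standard.** Section 8 also states: "Measurements will be performed according to the American Society of Echocardiography recommendations". It prints no alternative formula.

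**The concern.** The length to be cubed for the outer volume is the outer diameter: cavity plus septum plus posterior wall. Multiplying the walls gives an area, which cannot be added to a diameter. A relative wall thickness must be a pure number if it is to be judged against 0.41, and a product of two lengths divided by a length is not one. Separately, 1.04 should scale the myocardial volume (outer cube minus inner cube), but as bracketed it scales the outer cube alone.

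The LVH cuts and the 0.41 cut are fixed numbers. If the derived variables were programmed from this text, LVH status and type would be wrong for many participants. Continuous LVMI would also be distorted, because the error changes with wall thickness and is not a constant scale factor. The background (Section 3) names ventricular hypertrophy among the AF risks that such research should measure, so the variable should be right even though it is secondary.

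**Working it through.** The documents state no LV mass, LVH prevalence or power figure that rests on these formulas, so there is no plan figure to reproduce. The check is of units first and then of size.

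**Inputs from the plan:** the two printed formulas, centimetres, cuts of 49.2 (men) and 46.7 (women) g/m^2.7, and 0.41.

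**Inputs assumed (not in the documents):** LVIDd 4.5 to 5.5 cm, equal walls of 0.8 to 2.0 cm, height about 1.62 to 1.77 m.

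**1. Units.** Take LVIDd 5.0 cm and both walls 1.1 cm.
- Printed bracket from cm inputs: 5.0 + 1.1 × 1.1 = 6.21 cm.
- Printed bracket from mm inputs: 50 + 11 × 11 = 171 mm = 17.1 cm.
- Walls added: 5.0 + 1.1 + 1.1 = 7.2 cm in either unit.
- Printed wall ratio: 1.21/5.0 = 0.242 in cm, but 121/50 = 2.42 in mm. Walls added: 2.2/5.0 = 0.44 in either unit.

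**2. Placement of 1.04.** With zero wall thickness and LVIDd 5.0 cm, the printed formula returns 0.8 × (1.04 × 125 − 125) + 0.6 = 4.6 g. With 1.04 outside the difference it returns 0.6 g. The excess is 0.032 × LVIDd³ = 4.0 g, small beside the wall error and in the opposite direction.

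**3. Worked hearts.** Printed mass = 0.8 × [1.04 × (L + S × P)³ − L³] + 0.6. Summed mass = 0.8 × 1.04 × [(L + S + P)³ − L³] + 0.6.
- LVIDd 4.8 cm, walls 1.0 cm. Printed: 0.8 × [1.04 × 5.8³ − 4.8³] + 0.6 = 74.5 g. Summed: 0.8 × 1.04 × [6.8³ − 4.8³] + 0.6 = 170.2 g. Wall ratio 0.21 against 0.42.
- LVIDd 5.0 cm, walls 1.3 cm, man of 1.75 m (1.75^2.7 = 4.53). Mass 149.7 against 261.8 g; LVMI 33.0 against 57.8, on opposite sides of 49.2.

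**4. Ratio of printed to summed mass, LVIDd 4.5 to 5.5 cm.**

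| Both walls (cm) | Ratio |
|---|---|
| 0.8 | 0.36–0.38 |
| 1.0 | 0.43–0.45 |
| 1.1 | 0.47–0.49 |
| 1.2 | 0.52–0.53 |
| 1.3 | 0.56–0.58 |
| 1.5 | 0.67–0.68 |
| 2.0 | about 1.0 |

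**5. Wall thickness at which each cut is reached, LVIDd 5.0 cm.**
- LVH, man of 1.75 m: 1.51 cm printed, 1.16 cm summed.
- LVH, woman of 1.62 m: 1.37 cm printed, 0.96 cm summed.
- Wall ratio of 0.41: √(0.41 × 5.0) = 1.43 cm printed; 0.41 × 5.0/2 = 1.025 cm summed.

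**6. Simulated populations.** Eighteen assumed populations were run: mean septum 1.0 to 1.2 cm, posterior wall 0.05 cm thinner, wall SD 0.15 to 0.20 cm, mean LVIDd 4.7 to 5.3 cm, 60% men. The printed formulas missed 82% to 99% of the LVH found with summed walls, and 92% to nearly 100% of concentric LVH. Varying the unstated details (such as the spread of height and cavity size) moves the lower end for LVH to about 77%.

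**The case against.** **The operator may have been misread from the PDF.** This is possible and the source page should be checked. It is unlikely, because the multiplication sign appears in two separate formulas while the other plus signs in the LVMI expression were read correctly. The position of the 1.04 bracket is harder still to explain that way.

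**Nobody may have coded the typed line.** The plan cites a validated formula, refers to echocardiography society recommendations, and has an accredited laboratory measure off-line in echo software. This stands as a limit on the harm. It does not repair the text, which gives no other derivation.

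**The replacement for relative wall thickness is only partly derivable.** Twice the posterior wall over LVIDd would also be unitless, and the cited reference is not available here. This stands, and the fix allows for it.

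**Stronger readings that a reader might infer are not supported.**
- That concentric remodelling is missed: the plan applies 0.41 only to subjects with LVH and has no such class.
- That those still labelled LVH would mostly be called eccentric: at LVIDd 5.0 cm, a 1.75 m man who reaches printed LVH at 1.51 cm has a printed ratio of 1.51²/5.0 = 0.46, hence concentric. In simulation the eccentric share ran from about a third to nearly all, depending on the assumptions.
- That the structural-heart pathway would look absent: left atrial volume is the primary echo measure, and atrial pressure, atrial strain, appendage velocity and LVEF do not use these formulas.

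**Conclusion.** The formulas are wrong as written. Units and geometry alone show this, with no outside source. The size of the harm is conditional on literal coding and on assumed heart dimensions. At walls of 1.0 to 1.3 cm and LVIDd 4.5 to 5.5 cm, LV mass would be about 0.43 to 0.58 of the summed-wall value; the ratio is about 0.36 at 0.8 cm walls, and the understatement disappears near 2.0 cm. Most LVH and most concentric hypertrophy would be missed in every population tried.

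It would be too strong to say that the study's LV mass values are halved: nothing in the documents shows that the printed formula was used.

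The reach is limited. LVMI and LVH enter exploratory Aim 1a as secondary mediators and SA3 as secondary outcomes, and the plan says the SA3 assessment is not confirmatory. Neither is in the covariate list, so the adjusted SA1 models do not depend on them. No power figure does either.

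**What to change.** 1. Check the source page and the references cited for both formulas.
2. Correct item 4 to LVMI = {0.8 × 1.04 × [(LVIDd + IVST + LVPWT)³ − LVIDd³] + 0.6} / height^2.7.
3. Correct item 5 to a unitless relative wall thickness: (LVPWT + IVST)/LVIDd, or the form in the cited reference.
4. In Table 2 (Sections 9 and 10), attach the 0.41 cut to relative wall thickness, in line with item 5.
5. Confirm which formula the echo software or analysis program used. Recompute LVMI, LVH and LVH type from the stored dimensions only if it was the printed one.

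The cost is a few lines of protocol text and a check of the code. At worst, derived variables are re-run from measurements already taken, with no new data collection.
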